2.0 STUDY OBJECTIVES

The purpose is to prospectively study the feasibility to optimize configuration of CRT delivery for acute correction of electrical dyssynchrony using a noninvasive mapping of global electrical activation.

Study Hypothesis

Tailor-made configuration of CRT delivery is feasible and able to improve responder rate compare to single method of CRT delivery in candidates with known poor response to CRT.

Primary outcome measure

Responder rate of greater than 10% of LV end systolic volume reduction in patients undergoing tailor-made approach of CRT delivery at 6 months. The responder rate is to compare with pre-defined level of 40% for single method of CRT delivery namely biventricular pacing with LV lead in coronary sinus.

Secondary outcome measures

1. The acute electrical dyssynchrony indices of different methods of CRT delivery.
2. The hemodynamic responses of different methods of CRT delivery.
3. Procedure duration and implantation success rate of the optimal CRT delivery method as determined by the best improvement in electrical dyssynchrony indices.
4. Cine images (PA, LAO 30°, RAO 30°) and Chest X ray (PA view)
5. Peri-operative and 6 months follow-up complications rate:
 - a. Thromboembolic event
 - b. Dislodgement and migration of pacing leads
 - c. Phrenic nerve stimulation
 - d. Others
6. Echocardiogram parameters at baseline and 6 months: left ventricular systolic and diastolic volume, left ventricular ejection fraction, degree of mitral regurgitation, strain imaging.
7. NYHA class, 6 minute hall walk test and quality of life using Minnesota's questionnaire at baseline and 6 months.
8. Electrical parameters including threshold, sensitivity and lead impedance of pacing leads at implant and 6 months follow-up.

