Previous study on noninvasive activation pattern has shown that responders showed higher degree of baseline dyssynchrony and greater improvement of dyssynchrony by CRT when compared to nonresponders.¹⁷⁻¹⁹ The optimal configuration of CRT delivery is defined by that result in the greatest improvement of electrical dyssynchrony. The acute change in electrical dyssynchrony indices will be compare between the optimal configuration and the conventional configuration, namely biventricular pacing with single LV lead in posterior or lateral branch of coronary sinus. A significant different between the two configurations would suggest that there indeed is an optimal configuration of CRT delivery and a tailor made strategy is feasible. To prove this concept of tailor made strategy, devices will be implanted to deliver CRT using the optimal configuration determined by noninvasive electrical activation mapping in non-LBBB patients. The medium term improvement of surrogate marker of LV systolic volume will be compared to that of a predefined level of 40%.

Our group has been using echocardiogram to study mechanical dyssynchrony in patients with heart failure and pacing induced LV dysfunction in predicting response to CRT.³¹⁻⁴⁷ However, in subsequent multi-center trial studying 12 different echocardiographic parameters of mechanical dyssynchrony in predicting CRT response, no single echocardiographic measure of dyssynchrony was shown to improve patient selection for CRT.⁴⁸ The results of the study further strengthen the concept that the response to conventional CRT therapy cannot be predicted by baseline dyssynchrony pattern. It is rather the degree of improvement from baseline that will predict response to CRT therapy. The degree of dyssynchrony improvement on the other hand is determined by the interaction of baseline electrical substrate and the activation change brings about by CRT. The electrical substrate is fixed but different configuration of CRT delivery, including different location of LV lead, can produce different changes in activation. In order to study the interaction of electrical substrate and change in activation brings about by CRT, a tool that allows global electrical mapping of both the LV and RV is considered to be important not only to elucidate important information like location of conduction block but also to study the interaction of the left and right ventricle.^{17-19,22}

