5.0 STATISTICAL CONSIDERATION

Hypothesis

The null and alternative hypotheses are as follows:

H0: The responder rate of tailor-made approach \leq 40%

HA: The responder rate of tailor-made approach $>$ 40%

Sample size was calculated employing binomial methods with the following assumptions were used:

Expected responder rate for tailor-made approach =60%

Historical control responder rate =40%

Test significance level (a) = 0.05 (1-sided)

Power= 80%

Based on the above assumptions, the sample size was calculated as 77. Accounting for the attrition of 20%, the total required sample size is 93 patients with device implanted.

Statistical method for additional analysis

All continuous data will be summarized with the number of non-missing data, mean \pm standard deviation, median and range (minimum – maximum). T test will be used for the comparison between the groups. In case the assumption for t test is violated, then the equivalent nonparametric test, such as Wilcoxon rank sum test, Kolmogorov-smirnov test, will be used instead. The normality assumption will be tested by the normality test with the aid of QQ plot.

All categorical data will be tabulated with number of occurrence and percentage. Chi-square test will be used for the comparison between the groups. In case the expected counts in each cell is less than 5, then Fisher's exact test will be used instead.

Procedures for reporting any deviation(s) from the original statistical plan

Any deviations from the statistical analysis plan will be documented.

The treatment of missing, unused or spurious data, including drop-outs and withdrawals.

No imputation techniques will be used.

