All measurements will be made with an average of 10 second recordings with no occurrence of premature atrial or ventricular beats during the recording and 1 minute interval between changes in pacing settings.

During sinus rhythm and the 7 configurations of CRT pacing as stated above both noninvasive electrical activation map and acute hemodynamic measurement will be recorded for analysis.

Implantation of CRT device**1) Conventional pacing configuration**

The CRT system will be implanted with standard technique for conventional pacing configuration. Only market released CRT devices and leads will be implanted.

2) Epicardial LV pacing in the latest activation site

LV lead will be placed in the LV latest activation site or the site in closest proximity to the latest activation site and if necessary quadripolar or active fixation LV lead will be used to achieve stability.

3) Direct His-bundle pacing

i) In subjects in sinus rhythm

For direct-His bundle pacing, standard techniques will be used to place an LV lead preferably in the posterolateral branch of the coronary sinus system, RV and right atrial lead. His pacing lead (SelectSecure, model 3830, Medtronic Inc, USA) supported using a dedicated delivery sheath (model C315, Medtronic Inc, USA) or a deflectable lead delivery sheath (model C304, Medtronic Inc, USA) to the site showing His bundle signal on the mapping catheter. Multiple position to optimize QRS narrowing and threshold could be tested. The His pacing lead and the LV lead will be connected via a Y-adapter (model 5866-38M, Medtronic Inc, USA). The HBP will be connected to the cathode and the LV tip to the anode of the Y-connector.

ii) In subjects in AF

The same as for subjects in sinus rhythm except the His pacing lead will be connected to the atrial port of the CRT device and LV lead into the LV port of the CRT device without the use of a Y adapter.

4) Multiple point pacing

For multiple point pacing, the septal RV and the bipolar LV leads will be connected to the LV port using a parallel Y-adapter (model 2872, Medtronic Inc, USA) for the 2 RV leads group. Whilst the anterior bipolar and posterior/lateral LV lead will be connected using a parallel Y-adapter (model 2872, Medtronic Inc, USA) for the 2 LV leads group. If simultaneous pacing from 2 sites or the quadripolar LV lead pacing is the optimal configuration, a quadripolar lead will be connected to the LV port.

CRT programming

Para meter	Mandatory Device Setting
Mode	DDD or DDDR

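### The acute comparison of 7 or 8 pacing configurations has no listed contrasts, no secondary alpha, no multiplicity control and no exploratory label, and the tests named are two-group tests for data measured within the same patients

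*Combined protocol and SAP*

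**What the plan says.** Section 2.0 lists as secondary outcomes 1 and 2 the acute electrical indices and "The hemodynamic responses of different methods of CRT delivery". Section 6.0 defines five electrical indices (TAT, RVTAT, LVTAT, VEU and ED) and one hemodynamic measure, LV dP/dt.

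On the number of states, section 6.0 first announces 8 configurations and lists 1 + 1 + 3 + 3 = 8 under its four main headings. It later says: "During sinus rhythm and the 7 configurations of CRT pacing as stated above both noninvasive electrical activation map and acute hemodynamic measurement will be recorded". One listed configuration is tested only when its site differs from the conventional one. That may explain the two counts, but the text does not say so.

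Section 5.0 gives an alpha once, for the primary responder test: "Test significance level (a) = 0.05 (1-sided". For other continuous data it says "T test will be used for the comparison between the groups", with nonparametric substitutes such as the Wilcoxon rank sum and Kolmogorov-Smirnov tests. This stands under a heading for additional analysis. No contrasts, ordering, adjustment or exploratory status are stated.

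Section 1.0 describes one acute contrast, optimal against conventional on the electrical indices, and says how it would be read: "A significant different between the two configurations would suggest that there indeed is an optimal configuration of CRT delivery and a tailor made strategy is" (the last word, cut here, is feasible).

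**The concern.** Two things do not fit. First, the design gives repeated measurements on each patient under 7 to 9 states, but the tests named each compare two groups. They cannot describe the whole comparison, and as named they ignore that the same patients supply every state.

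Second, nothing limits how many two-state comparisons are made or how they are interpreted. The acute study is where readers would look to learn whether His-bundle, triple-site or latest-site pacing outperforms conventional pacing. With six measures and at least six alternatives to conventional pacing, an unadjusted significant result is easy to obtain by chance, and the plan gives no rule for telling a planned finding from a chance one.

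**Working it through.** **Inputs from the documents.** 7 or 8 configurations plus sinus rhythm (section 6.0); five electrical indices and LV dP/dt (section 6.0); 77 evaluable patients and 93 in total (section 5.0). The plan states no error rate for the acute comparisons, so there is no figure of its own to reproduce on this point.

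The patient number was checked: "Based on the above assumptions, the sample size was calculated as 77". With 60% against 40%, one-sided 0.05 and 80% power, the two-group formula gives (1.645 × √(2 × 0.5 × 0.5) + 0.842 × √(0.24 + 0.24))² / 0.2² = 76.2, so 77 per group. That this is a two-group formula for a one-sample hypothesis is a separate matter. Here 77 and 93 serve only as patient counts.

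**Assumptions not in the documents.** Two-sided 0.05 per test; equal true means in all states; equal correlation between states within a patient.

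**Step 1: number of tests per measure.** With K states there are K − 1 contrasts against conventional pacing and K(K − 1)/2 pairs. K = 7 gives 6 and 21; K = 8 gives 7 and 28.

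**Step 2: paired t tests, LV dP/dt alone.** Simulated chance of at least one false positive (8,000 trials per row):

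| K | Patients | Any false difference from conventional | Falsely better than conventional | Any false difference, all pairs |
|---|---|---|---|---|
| 7 | 77 | 0.208 | 0.103 | 0.442 |
| 7 | 93 | 0.217 | 0.108 | 0.445 |
| 8 | 77 | 0.224 | 0.107 | 0.508 |
| 8 | 93 | 0.232 | 0.116 | 0.515 |

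As a check on the last column, the chance that the studentized range of K means exceeds √2 × 1.96 = 2.77 is 0.440 for K = 7 and 0.509 for K = 8. Separate simulation runs gave up to 46% and 52%. The independence formula 1 − 0.95^m gives 66% (m = 21) and 76% (m = 28), which is too high because the pairs share states.

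If the primary test's one-sided 0.05 were carried over, the chance of a false finding of superiority over conventional pacing would be 19% to 20%.

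**Step 3: two-sample tests on the same data.** With within-patient correlation ρ, the true variance of a difference in means is 2σ²(1 − ρ)/n, while the two-sample test uses 2σ²/n. Its standard error is too large by a factor 1/√(1 − ρ). The documents give no ρ, so a range is shown for 77 patients:

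| ρ | Standard error inflated by | Any false difference from conventional (K = 7 to 8) | All pairs (K = 7 to 8) |
|---|---|---|---|
| 0.3 | 1.20 | 9% to 10% | 23% to 28% |
| 0.5 | 1.41 | 3% to 4% | 8% to 11% |
| 0.8 | 2.24 | near 0% | near 0% |

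The lower rates come from wrong standard errors. The same inflation hides real differences.

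**Step 4: several measures.** Even if each measure is held at 5%, six independent measures give 1 − 0.95⁶ = 26%. The acute measures are probably correlated, so this is only a guide, but it shows why adjusting contrasts within each measure is not enough.

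**Step 5: thresholds under adjustment.** Under Holm the smallest p-value must be at most 0.05/6 = 0.0083 or 0.05/7 = 0.0071.

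**The case against.** A reader might infer that the plan tests every pair of configurations at the full 5% level, so that a false winner on LV dP/dt is about as likely as not. The documents do not support that. They describe no all-pairs analysis and give no alpha for secondary tests. Sinus rhythm, which enters the 8-state figure when 7 configurations are counted, is not a CRT configuration. The only comparator named is conventional pacing, for which the risk is about 21% to 23%, or about half that in the favorable direction.

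A reader might also infer that section 1.0 hangs a conclusion on LV dP/dt. It does not: that conclusion belongs to optimal against conventional on the electrical indices. The optimal configuration is likewise defined by the electrical indices, so a false positive on LV dP/dt would not change which device configuration is chosen.

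It is also fair to say that these are secondary outcomes in a single-center, non-randomized feasibility study, and that multiplicity control is often not demanded there. In that case the plan should call them exploratory, and it does not.

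Finally, the trial asks whether the best configuration varies between patients. Average differences could be nil while tailoring still helps. This stands as a limit on what average contrasts can show, and it is a reason not to make the contrasts depend on an overall test. It does not justify unadjusted two-group tests of those averages.

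**Conclusion.** The point holds as a gap in the analysis of secondary outcomes 1 and 2. The named tests do not match the within-patient, multi-state design, and the number of comparisons is neither fixed nor controlled. On LV dP/dt alone the false-positive risk is about four times 5% if each alternative is compared with conventional pacing by paired tests. The all-pairs figure is an upper scenario and not the plan's stated method. Both rest on two-sided 0.05 per test and equal true means. Two-sample tests would lower the rate by an amount set by a correlation the documents do not give, at the cost of invalid standard errors and lost power.

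The primary responder test is a single test of a separate 6-month outcome, and its type I error is untouched.

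One related problem lies outside this point. The optimal configuration is the one with the greatest electrical improvement, so comparing it with conventional pacing on the same indices is favorable by selection. Multiplicity adjustment does not cure that.

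**What to change.** In section 5.0, replace the between-groups tests for outcomes 1 and 2 with the following.

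1. Analyze each acute measure in one repeated-measures model, with patient as random effect and configuration as factor. If the data are clearly non-normal, use a Friedman test with paired signed-rank contrasts. The Friedman test needs every state in every patient, so say how it treats the configuration that is tested only in some patients.
2. Test each other configuration against conventional biventricular pacing with Holm or Dunnett adjustment. No preceding overall test is needed, because the adjustment already controls the error rate within the measure.
3. Name one lead acute measure, or adjust across all six.
4. Report all other contrasts as exploratory estimates with 95% confidence intervals and no claim of significance.
5. Reconcile the counts of 7 and 8 configurations in section 6.0, so that the number of contrasts is fixed in advance.

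The cost is SAP wording and a little more analysis; no patients, measurements or procedures are added. The downside is a stricter threshold: the smallest of 6 or 7 p-values must reach about 0.008 or 0.007 under Holm, and adjusting across measures tightens this further, so a weak difference may no longer be called significant.

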6.0 PROTOCOL DESCRIPTION

Patient informed consent

The investigator is responsible for obtaining informed consent from each prospective study patient prior to the performance of any study related procedures. After a patient has been provided with the information of the study and given time to think on whether to participating into the study, the patient will be asked to sign and date a consent form. One copy of the signed patient consent form must be handed out to the patient and one must be filed by the investigator in the investigator files. After the patient and the investigator have signed and dated the consent form, the study data collection process may start.

Patients meeting all the inclusion criteria and not meeting any of the exclusion criteria are eligible for the study. Data will be collected at the following study visits:

Enrollment

Noninvasive electrical activation and acute hemodynamic study

Implant

[figure not shown]
Pre-discharge (PDH) (\leq 72 hours post implant)

Month 3 follow-up visit: 90 ± 14 days post implant

Month 6 follow-up visit: 180 ± 14 days post implant

Table 1. Data collection for each scheduled visit

	Enrollment	Implant *	PDH*	Month 3	Month 6
Patient Informed Consent	x				
Echocardiogram	x		x	x	x
Medical History	x				
Cardiovascular Medication	x	x	x	x	x
NYHA Class	x			x	x
6MHW	x			x	x
SF-36QoL	x			x	x
12-lead electrocardiogram	x	x		x	x
Cine images		x			
Device Interrogation		x	x	x	x
Adverse Event	x	x	x	x	x
Protocol Deviation	x	x	x	x	x

Figure 1. Study Flow Chart

Noninvasive mapping of electrical activation

Ventricular activation maps will be acquired simultaneously with hemodynamic measurements using noninvasive mapping system (ECVUE, Medtronic Inc, USA). A thoracic computed tomographic scan will be acquired with the electrodes attached to the patient. Local ventricular activation times will be defined as the onset of the QRS complex or the pacing spike to the maximal negative slope of each unipolar electrogram.

The following electrical dyssynchrony indices will be derived

- i) Total activation time (TAT) is defined as the time difference between the earliest and latest site of activation on the entire ventricular epicardium (LV and RV);
- ii) RVTAT is defined as the time difference between the earliest and latest site of activation on the RV ventricular epicardium;
- iii) LVTAT is defined as the time difference between the earliest and latest site of activation on the LV ventricular epicardium;

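### Month 3 echo and walk data are scheduled for every patient, but no outcome or inferential analysis uses them, so patients lost after month 3 add nothing to the 6-month secondary estimates

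*Combined protocol and SAP*

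**What the plan says.** Section 6.0 fixes an interim visit, "Month 3 follow-up visit: 90 ± 14 days post implant". The table headed "Table 1. Data collection for each scheduled visit" marks echocardiogram, NYHA class, 6-minute walk and a quality-of-life form at enrollment, month 3 and month 6, with no restriction to a subset of patients. Echocardiography is also marked at pre-discharge.

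The outcomes in section 2.0 do not use the interim visit. Outcome 6 is "Echocardiogram parameters at baseline and 6 months". Outcome 7 is "NYHA class, 6 minute hall walk test and quality of life using Minnesota's questionnaire at baseline and 6 months". The primary outcome is also a 6-month measure.

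Section 5.0 has three provisions that bear on this point:
- For description: "All continuous data will be summarized with the number of non-missing data".
- For testing continuous data: "T test will be used for the comparison between the groups", with rank-based alternatives.
- For missing data, in full: "No imputation techniques will be used".

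The sample size allows for 20% attrition and is set at 93 implanted patients. No paired, change-from-baseline or repeated-measures analysis is named.

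**The concern.** The month 3 value of a volume or walk distance is likely to be informative about the same patient's month 6 value, and the trial will already hold it. An estimate built only from patients with a 6-month measurement discards that information.

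The study is non-randomized and the plan names no concurrent control for the 6-month outcomes, so selective loss is not offset by similar loss in another arm. Patients are NYHA class III or above, and section 6.0 lists death and withdrawal by the investigator among the ways participation ends. Loss related to worsening is therefore plausible. If it happens, the reported mean improvement is too large.

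This point is about the mean changes in outcomes 6 and 7. It is not about how missing patients count in the primary responder rate.

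**Working it through.** **Patients affected.** The plan's total reproduces as 77 × 1.2 = 92.4, rounded up to 93. With 20% lost, 93 × 0.8 = 74.4. About 74 patients have 6-month data and about 19 do not.

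**Assumed inputs.** The documents give none of these:
- SD of percent change in LV end-systolic volume: 20 points.
- Correlation ρ between month 3 and month 6 change: 0.5 to 0.8.
- Rise in log-odds of loss per SD of worse month 3 change: 0.5 to 1.0.
- Share of losses that occur after month 3: varied from all to none. Losses before month 3 are taken as random.

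**Bias of the observed-case mean.** If loss depends on the month 3 change, then bias = ρ × SD × m. Here m is the shift in the mean standardized month 3 change among patients who stay.

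Simulated overstatement of the mean reduction when all loss follows month 3 (93 patients, 4,000 trials per cell):

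| ρ | log-odds 0.5 | log-odds 1.0 |
|---|---|---|
| 0.5 | 0.9 | 1.7 |
| 0.7 | 1.3 | 2.4 |
| 0.8 | 1.5 | 2.8 |

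Numerical integration of the logistic loss model at 20% gives m = 0.096 and 0.173. The smallest cell is then 0.5 × 20 × 0.096 = 0.96 and the largest 0.8 × 20 × 0.173 = 2.77. Both agree with the table to within simulation error.

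If half the loss is early and random, 10% go before month 3. A further 0.10/0.90 = 11.1% of those remaining are lost depending on month 3. Then m = 0.054 and 0.100, and the bias runs from 0.5 × 20 × 0.054 = 0.5 to 0.8 × 20 × 0.100 = 1.6 points. With three quarters of the loss early, it is 0.3 to 0.9 points.

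**Scale.** The standard error with 74 patients is 20/√74 = 2.3 points. The all-late bias is 0.9/2.3 = 0.4 to 2.8/2.3 = 1.2 standard errors. In SD units it is 0.9/20 = 0.05 to 2.8/20 = 0.14, which carries over to ejection fraction, strain or walk distance under the same correlation and loss assumptions.

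**With month 3 used.** A likelihood estimate that uses the month 3 values had bias below 0.1 point in the same simulations.

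**Precision when loss is unrelated to month 3.** The variance is SD² × [(1 − ρ²)/n6 + ρ²/n3], where n6 and n3 are the numbers seen at each visit. The proportional reduction is ρ² × (1 − n6/n3).
- All losses seen at month 3 (n3 = 93): 1 − 74/93 = 0.204, so 0.25 × 0.204 = 5% to 0.64 × 0.204 = 13%. The simulated variance ratio of up to 1.16 gives 1 − 1/1.16 = 14%.
- Half seen (n3 = 83.5): 1 − 74/83.5 = 0.114, so 3% to 7%.
- None seen (n3 = 74): zero.

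**The case against.** Several stronger readings are tempting and go further than the documents.

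- **The plan tests 6-month changes on completers.** It does not say so. The reference to non-missing data means that the count is reported, and the t test is between groups. Observed-case analysis is an inference from having no imputation and no model. The inference is reasonable, because nothing in section 5.0 would use a partial record, but it is not plan text. No test of change from baseline is specified at all, which is itself a gap.
- **Month 3 data go unused.** The general rule to summarize continuous data and tabulate categorical data would cover month 3 descriptively. Only an outcome or inferential use is missing.
- **Quality of life and NYHA class are affected in the same way.** Outcome 7 names the Minnesota questionnaire while Table 1 lists SF-36, so as written there is no month 3 score on the outcome's own instrument. NYHA class is ordinal, and a model for continuous measures does not serve it.
- **The full 20% is recoverable.** The allowance applies to implanted patients and the plan gives no timing, so early losses are included. With mixed timing the bias is below one standard error.
- **The bias is 7% to 21% of the effect.** That takes an assumed mean change of −13. With SD 20 and normal data, the plan's 60% responder rate needs about −15, which makes it 0.9/15 = 6% to 2.8/15 = 19%.

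Two further objections stand. A likelihood model estimates what patients who died would have shown had they been measured, so it does not settle how deaths are handled. Also, the simulation used percent changes, whereas a model on raw volumes gives an absolute change; the scale therefore has to be specified.

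It can also be argued that secondary outcomes of a feasibility study do not need this. That limits the priority of the change, but does not make discarding scheduled data the better choice.

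**Conclusion.** The point holds for the continuous echo measures and walk distance. Month 3 values are scheduled in every patient, no outcome or named inferential analysis uses them, and patients lost after month 3 drop out of the 6-month estimates.

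Under the stated assumptions, the mean reduction in end-systolic volume is overstated by 0.9 to 2.8 points if all loss follows month 3 and by 0.5 to 1.6 if half does. If no loss follows month 3, any bias cannot be corrected from these data. The variance gain is 0% to about 14%. The SD, correlation, loss mechanism and timing are all assumed, so the direction of the bias is better supported than its size.

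The responder rate and its test are outside this point.

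**What to change.** In section 5.0, for the continuous measures in outcome 6 and for walk distance in outcome 7:

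1. Estimate the 6-month change from baseline with a mixed model for repeated measures. Use baseline, month 3 and month 6 as visits, with an unstructured covariance, and report a 95% interval. Model volumes on the log scale if percent change is to be reported.
2. Keep the observed-case paired change as a sensitivity analysis.
3. Report deaths separately, and state that the model's estimate for patients who died is hypothetical.
4. Extend the model to quality of life only after the Minnesota and SF-36 passages are reconciled. Leave NYHA class out of this model.

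The model is not imputation, so it is consistent with the plan's missing-data rule. The cost is SAP wording and a little more analysis work, with no new visits or data. The price in assumptions is missing at random: given the observed values, loss must not depend on the unseen 6-month value.

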- iv) Ventricular electrical uncoupling (VEU) is defined as mean LV activation time minus mean RV activation time (LVTAT-RVTAT)
- v) Intra-LV electrical dyssynchrony index (ED) is the standard deviation of activation times at 500 sites on the LV epicardium, including the epicardial aspect of the septum.

Placement of electrophysiology catheters for CRT delivery

Pacing leads will be placed in high right atrium, His-bundle region, right ventricular apex, high septal RV, coronary sinus posterior/lateral branch, coronary sinus anterior branch, lateral and septal region of endocardial LV in order to deliver CRT in 8 different configurations as stated below:

- 1) Conventional biventricular pacing with RV lead in right ventricular apex and LV lead in lateral or posterior branch of coronary sinus
- 2) Biventricular pacing with the LV lead in coronary sinus in closest possible proximity to the latest electrical activation region (18 region) if it is different to the site tested in (1)
- 3) Direct His-bundle pacing
 - i) His bundle pacing catheter distal tip as cathode and RV lead proximal pole as anode
 - ii) His bundle pacing catheter distal tip as cathode and proximal pole of LV lead placed in lateral or posterior branch of coronary sinus as anode.
 - iii) His bundle pacing catheter distal tip as cathode and His bundle pacing catheter proximal pole as anode.

In subjects in sinus rhythm

- i) together with RV bipolar pacing with RV lead in RV apex.

In subjects in AF

- i) together with RV bipolar and LV bipolar pacing

4) Multi-point pacing

- i) Triple site pacing with two RV leads in the RV apex and high RV septum and LV lead in posterior or lateral branch of coronary sinus.
- ii) Triple site pacing with RV lead in the RV apex and one LV lead in posterior or lateral branch of coronary sinus and the other LV lead in anterior branch of coronary sinus.
- iii) Triple site pacing with RV lead in RV apex and one quadripolar LV lead in posterior or lateral branch of coronary sinus and pacing at 2 sites simultaneously from the quadripolar lead.

During delivery of CRT the output will be set at twice the capture threshold and pacing impulse will be delivered in VDD mode with an AV delay of 80msec and VV delay at 0msec for all leads in the ventricles.

Acute hemodynamics studies

Invasive LV hemodynamic measurements of LV dP/dt will be recorded using a micromanometer (Radi Medical Systems, St Jude Medical, USA) placed in the LV cavity.

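### Secondary outcome 7 names the Minnesota questionnaire, but Table 1 schedules only SF-36; a smaller point is that the words and the bracketed formula for VEU define different quantities

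*Combined protocol and SAP*

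**What the plan says.** **Quality of life.** Section 2.0, secondary outcome 7, lists NYHA class, the 6-minute walk and "quality of life using Minnesota's questionnaire at baseline and 6 months". In Section 6.0, the schedule headed "Table 1. Data collection for each scheduled visit" has a single quality-of-life row, labelled SF-36, marked at enrollment, month 3 and month 6. The Minnesota questionnaire is named only in Section 2.0 and SF-36 only in Table 1.

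**VEU.** In Section 6.0, under noninvasive mapping, index (iv) reads "Ventricular electrical uncoupling (VEU) is defined as mean LV activation time minus mean RV activation time (LVTAT-RVTAT", where the bracket closes. Indices (ii) and (iii) on the same list define the two terms in that bracket: "RVTAT is defined as the time difference between the earliest and latest site of activation on the RV ventricular epicardium", and "LVTAT is defined as the time difference between the earliest and latest site of activation on the LV ventricular epicardium".

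**The concern.** **Quality of life.** Table 1 is what site staff work from. It does not leave quality of life blank; it tells them to give a different questionnaire. A team following it would not obtain a Minnesota score before implant, and a pre-implant score cannot be collected afterwards.

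The baseline matters here because the study is non-randomized (Section 4.0) and its primary comparison is with a fixed 40% responder rate (Section 5.0). No concurrent control group is planned, so any statement about quality of life rests on each patient's change from baseline. Section 5.0 also rules out imputation, so missing baselines would stay missing. Reporting SF-36 in place of the named instrument would replace the outcome measure.

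**VEU.** An analyst who follows the words and one who follows the bracket would report different quantities under the same name. VEU is one of the five dyssynchrony indices behind secondary outcome 1. Section 1.0 and secondary outcome 3 tie the optimal configuration to improvement in dyssynchrony without saying which index decides, so the documents do not show whether VEU also bears on the configuration implanted.

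**Working it through.** The plan gives no figure of its own to reproduce on either point.

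**(a) Outcomes 6 and 7 against Table 1**

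Outcome 6 is introduced as "Echocardiogram parameters at baseline and 6 months", and outcome 7 uses the same two times. Together they set four assessments at baseline and 6 months.

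| Assessment | Outcome list (2.0) | Table 1 (6.0), enrollment and month 6 | Match |
|---|---|---|---|
| Echocardiogram | outcome 6 | scheduled at both | yes |
| NYHA class | outcome 7 | scheduled at both | yes |
| 6-minute walk | outcome 7 | scheduled at both | yes |
| Quality of life | outcome 7, Minnesota | scheduled at both, but SF-36 | no |

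- Three of the four agree. For the fourth, the visits agree and only the instrument differs.
- Assessments per patient: Table 1 schedules 3 SF-36 (enrollment, month 3, month 6) and 0 Minnesota. Outcome 7 calls for 2 Minnesota (baseline, 6 months).
- Baseline scores at risk: Section 5.0 says "the total required sample size is 93 patients with device implanted". With one baseline score each, 93 × 1 = 93. This is an upper figure, reached only if Table 1 is followed to the letter in every patient.

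**(b) The two versions of VEU**

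- By the words: VEU = mean(LV times) − mean(RV times).
- By the bracket: VEU = [max(LV) − min(LV)] − [max(RV) − min(RV)].

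Adding a constant delay *d* to every LV time raises the worded version by *d* and leaves the bracket unchanged, because a shift does not alter a range. The two cannot be equivalent.

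Numerical illustration follows. The activation times are assumed, not taken from the documents, and evenly spread within each ventricle, so the mean is the midpoint.

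| Assumed times (ms) | Means, LV and RV | Ranges, LV and RV | By the words | By the bracket |
|---|---|---|---|---|
| LV 40–120, RV 0–80 | 80 and 40 | 80 and 80 | 80 − 40 = 40 | 80 − 80 = 0 |
| LV 0–120, RV 20–100 | 60 and 60 | 120 and 80 | 60 − 60 = 0 | 120 − 80 = 40 |

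A separate check with three sites per ventricle agrees:

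- LV {60, 80, 100} and RV {20, 40, 60}: words 80 − 40 = 40; bracket 40 − 40 = 0.
- LV {40, 60, 80} and RV {10, 60, 110}: words 60 − 60 = 0; bracket 40 − 100 = −60.

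These cases show that the versions differ. They say nothing about how often or by how much they would differ in the patients enrolled.

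**The case against.** **Table 1 is not a complete list.** The visit list includes "Noninvasive electrical activation and acute hemodynamic study", which has no column in Table 1. Chest X-ray (outcome 4) and procedure duration (outcome 3) have no row. Absence from the table is therefore weak evidence that something will not be collected. This stands as a limit: the loss is a risk, not a certainty. It does not remove the contradiction, because here the table names a different instrument rather than staying silent.

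**Something not visible might settle it.** The study flow chart (Figure 1) is not shown in the text available, and the asterisks on two Table 1 column heads have no visible note. Either might show which instrument was meant. Neither could make the outcome list and Table 1 agree as they are now worded.

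**The stakes are small.** Only the responder rate is powered, no success criterion is attached to quality of life, and SF-36 would still measure it at both time points. All true, and the reason this is not a major defect. It is still worth correcting, since the correction is small and a missed baseline cannot be recovered.

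**The VEU point is a clarification.** Largely agreed. Section 6.0, under acute hemodynamics, has the activation maps recorded for analysis, so either version can be recomputed later for outcome 1. That does not help if VEU has already informed the choice of configuration. It is also fair that the definition appears only once, so deleting the bracket changes it for every use. The role of VEU should therefore be settled first.

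**Conclusion.** Both points hold.

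The quality-of-life conflict should be corrected before enrollment. It affects one of three measures in one of eight secondary outcomes and does not touch the primary endpoint or the sample size. The figure of up to 93 missing pre-implant Minnesota scores assumes that Table 1 is followed throughout and that all planned patients receive a device. That the two places conflict is certain on the text available; that data would be lost is not.

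The VEU definition is wrong as written, since its words and its formula are different quantities, but on its own it is minor. The 40 ms gaps rest on assumed activation times and prove non-equivalence only.

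**What to change.** **(a)** Before enrollment, name the same instrument in Section 2.0 and in Table 1. There are two ways:

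- Add a Minnesota row to Table 1, at least at enrollment and month 6. This keeps the stated outcome and adds a questionnaire at visits already planned.
- Change outcome 7 to SF-36. This is one phrase of text, but it changes the outcome instrument and should be recorded as such.

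**(b)** For reporting outcome 1, keep a single VEU formula: delete the bracketed LVTAT-RVTAT so that the worded definition stands. First state whether VEU helps select the implanted configuration. If it does, Section 1.0 and the index definitions in Section 6.0 must be reconciled before mapping begins. Which version should guide selection is for the investigators to settle.

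**Cost:** a minor amendment covering one table row or one phrase, plus one bracket. No extra visits, and no change to the sample size or the primary analysis.
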